# 7.2.7 Serious Adverse Events

An SAE is any event that meets any of the following criteria:

- Death
- Life-threatening
- Inpatient hospitalization or prolongation of existing hospitalization
- Persistent or significant disability/incapacity
- Congenital anomaly/birth defect not present at Screening
- Other: Important medical events that may not result in death, be life-threatening, or require hospitalization, may be considered an SAE when, based upon appropriate medical judgment, they may jeopardize the participant and may require medical or surgical intervention to prevent one of the outcomes listed in this definition (e.g., intensive treatment in an emergency room or at home for allergic bronchospasm)

# 7.2.7.1 Definition of Terms

Life-threatening: An AE is life-threatening if the participant was at immediate risk of death from the event as it occurred; i.e., it does not include a reaction that if it had occurred in a more serious form might have caused death. For example, drug induced hepatitis that resolved without evidence of hepatic failure would not be considered life-threatening even though drug induced hepatitis can be fatal.

Hospitalization: is defined by the Sponsor as an admission to hospital for diagnosis and treatment requiring an overnight stay. Prolongation of an existing inpatient hospitalization due to an event also meets the regulatory criteria of an SAE.

Examples of visits to a hospital facility that do not meet the serious criteria for hospitalization include:

- Emergency room visits (that do not result in a full hospital admission)
- Preplanned or elective procedures prior to trial enrollment (e.g., outpatient surgery)
- Protocol procedures

Hospitalization signifies that the participant has been detained (usually involving at least an overnight stay) at the hospital or emergency ward for observation and/or treatment that would not have been appropriate in the physician's office or outpatient setting. When in doubt as to whether hospitalization occurred or was necessary, the AE should be considered serious.

Hospitalization planned prior to trial enrollment (e.g., for elective surgery or routine clinical procedures) that are not the result of AE (e.g., elective surgery for a pre-existing condition that has not worsened) need not be considered AEs or SAEs. If anything untoward is reported

during the procedure, that occurrence must be reported as an AE, either serious or non-serious according to seriousness criteria described in Section 7.2.7.

Disability/incapacitating: An AE is incapacitating or disabling if the experience results in a substantial and/or permanent disruption of the participant's ability to carry out normal life functions.

Severity is not the same as seriousness. Severity, or intensity, refers to the extent to which an AE or SAE affects a participant's daily activities. Seriousness must be equal to at least one of the criteria listed in Section 7.2.7 above.

# 7.2.7.2 Reporting Serious Adverse Events

[figure not shown]
Any AE that meets SAE criteria (Section 7.2.7) must be reported via EDC immediately (within 24 hours of knowledge by the Investigator). Regardless of causality, severity, and whether the participant has undergone any trial-related procedures, all SAEs must be reported and will be collected and recorded from the time the participant signs the consent form until 30 days following the final follow-up visit.

The initial report in the EDC should include at least the following information:

- Trial number
- Participant's identification number
- Description of the event
- Date and time of onset of the event
- Seriousness criteria
- Severity
- Investigator's assessment of Causality to the IP
- Participant's event outcome, as currently known

When additional information regarding an SAE is brought to the attention of the Investigator, this information should be entered into EDC. Examples would include but are not limited to the following:

- Signs and symptoms initially reported for which there is now a diagnosis leading to a change in the reported term
- Laboratory test results
- Outcome of the SAE
- Change in Investigator causality assessment due to results of further investigations

The Sponsor or designee will be responsible for ensuring Suspected Unexpected Serious Adverse Reaction are reported to IRBs/IEC per local requirements. These activities may be delegated by the Sponsor to their vendor and will be documented in the Safety Monitoring Plan.

Pregnancy in and of itself is not an SAE but all pregnancies should be reported in the same manner and timeframe as SAEs as described in Section 7.2.7. Complications of the pregnancy should be reported within 24 hours of knowledge by the Investigator (e.g., if the mother is hospitalized for dehydration) as an SAE. Pregnancies will be followed by the Sponsor to full term and beyond. Pregnancy terminations/abortions must be reported as an SAE.

# 7.2.8 Overdose

In the event of overdose, the participant should be observed, and any needed treatment required will be at the discretion of the Investigator. There is no known specific treatment in case of overdose.

Any instance of overdose must be communicated to the Sponsor or Medical Monitor within 24 hours and should be reported as an SAE. Details of any signs or symptoms and their management should be recorded including details of any treatments administered.

# 7.2.9 Contraception Requirements and Pregnancy

# 7.2.9.1 Contraception Requirements

Females (assigned at birth) must agree to use an acceptable form of contraception from the time of signing informed consent and through 24 weeks after the last dose of IP. Males (assigned at birth) must agree to use (or have their partner use) an acceptable form of contraception from the time of signing informed consent and through 24 weeks.

Acceptable methods of contraception (as applicable per local practices and regulations) are intrauterine device, diaphragm with spermicide, contraceptive sponge, condom, vasectomy (that takes place at least 12 weeks prior to Screening, with documentation of azoospermia), and any registered and marketed hormonal contraceptives that contain an estrogen and/or a progestational agent (including oral, subcutaneous, intrauterine, or intramuscular agents).

Participants do not require contraception if they are highly unlikely to become pregnant or to impregnate a partner since they meet at least 1 of the following criteria:

- A female (as assigned at birth) participant who is not of reproductive potential is eligible without requiring the use of contraception. A female participant who is not of reproductive potential is defined as: one who has either (1) reached natural menopause (defined as 12 months of spontaneous amenorrhea); (2) 6 weeks post-surgical bilateral oophorectomy with or without hysterectomy; or (3) bilateral tubal ligation. Spontaneous amenorrhea does not include cases for which there is an underlying disease that causes amenorrhea (e.g., anorexia nervosa).
- A male (as assigned at birth) or female (as assigned at birth) participant who is of reproductive potential agrees to remain abstinent or use (or have their partner use) 2 acceptable methods of birth control starting at enrollment and through the 24-week trial period.

# 7.2.9.2 Pregnancy

Although pregnancy is not always considered an AE or SAE by regulatory definition, for this trial, pregnancies in any participant or in the partner of a male participant receiving at least 1 capsule of IP must be reported in the same manner as SAEs using the Pregnancy Reporting Form.

Any pregnancy complication, or elective termination of a pregnancy for medical reasons, will be recorded as an AE or, if appropriate, an SAE.

The Investigator must submit the Pregnancy Reporting Form immediately (within 24 hours) after the pregnancy is confirmed. If the participant has received the IP prior to becoming pregnant, the participant will continue the efficacy and safety assessment until 6 months after live birth or 24 weeks after the last dose of IP, whichever is longer.

The participant should be followed until the outcome of the pregnancy is determined. It is the responsibility of the Investigator to obtain and document pregnancy information on the most recent Pregnancy Report Form. Furthermore, any SAE occurring as outcome of the pregnancy must be reported per the SAE Reporting procedures (Section 7.2.7.2).

Should pregnancy occur in a partner, the same SAE pregnancy reporting procedures should be followed. The participant may continue in the trial.

# 7.2.10 Vital Signs, Height, and Weight

Vital signs (temperature, heart rate, respiratory rate, blood pressure, and pulse oximetry) will be assessed per SOC as listed in the Schedule of Assessments (Table 3 and Table 4). Vital signs will be measured before IP administration when applicable. Vital sign measurement at Week 24 is at the discretion of the Investigator.

Body weight and height will be measured per SOC. Height and weight will be used to calculate body mass index (BMI). Height and weight for wheelchair-bound participants is optional. Height is only required at Day 1.

Pre-CDI BMI will be collected as part of the participant's medical history.

Any vital sign abnormality that is judged by the Investigator as clinically significant (except at the Screening visit) will be considered an AE, recorded on the CRF, and monitored as described in Section 7.2.3.

# 7.2.11 Physical Examinations

A physical examination (including evaluation of general appearance/mental status; head, eyes, ears, nose, throat; and the following body systems: skin, heart, lungs, abdomen, and extremities) will be performed at the time points listed in the Schedule of Assessments (Table 3 and Table 4).

Any physical examination finding that is judged by the Investigator as clinically significant (except at the Screening visit) will be considered an AE, recorded on the CRF, and monitored as described in Section 7.2.3. Investigators should pay special attention to clinical signs related to previous serious diseases.

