# 7.2.2 Definition of Adverse Events

An AE is an untoward medical occurrence in a clinical investigation participant administered a pharmaceutical product and which does not necessarily have to have a causal relationship with this medicinal product. An AE can therefore be any unfavorable and unintended sign (including an abnormal laboratory finding, for example), symptom, or disease temporally associated with the use of the medicinal product, whether or not considered related to the medicinal product.

AEs may include, but are not limited to:

- Subjective or objective symptoms spontaneously offered by the participant and/or observed by the Investigator or medical staff.
- Findings at physical examinations.
- Laboratory abnormalities of clinical significance.

Disease signs, symptoms, and/or laboratory abnormalities already existing prior to the use of the IP are not considered AEs after treatment unless they reoccur after the participant has recovered from the pre-existing condition, or in the opinion of the Investigator, they represent a clinically significant exacerbation in intensity or frequency.

If clinically significant worsening from baseline is noted, the changes will be documented as AEs on the AE page of the CRF. Clinical significance is defined as any variation in signs, symptoms, or testing that has medical relevance and may result in an alteration in medical care. The Investigator will continue to monitor the participant until the assessment returns to baseline or until the Investigator determines that follow-up is no longer medically necessary.

Investigators should inform the Sponsor regarding any event that seems unusual, even if this event may be considered an unanticipated benefit to the participant.

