# 8.5.2 Adverse Events

Any AE reported on the CRF that occurs during or post the administration of IP is defined as TEAE. Additionally, it will be assumed that an AE that was reported to have started at Randomization (Day 1) without an associated onset time may have occurred after the administration of IP. Hence, AEs occurring at Randomization (Day 1) with no associated onset time are assumed to be treatment-emergent.

For the primary safety endpoint, the incidence rate of TEAEs will be presented by treatment group through Week 8.

For the other safety endpoints, the incidence rate of TEAEs and TESAEs will be presented by treatment group through Week 24.

In addition, an overview of TEAEs will be provided which summarizes the incidence of the following information:

- All TEAEs
- Drug-related TEAEs
- Maximum severity of TEAEs
- Deaths
- SAEs

The number and percentage of participants who experienced at least 1 TEAE will be presented by MedDRA system organ class and preferred term. Drug-related TEAEs, withdrawals due to TEAEs, and all SAEs will be summarized in the same manner.

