- 7. For the Qualifying CDI episode, the participant will have received SOC CDI antibiotics (10-21 days: with exact duration, antibiotic type, and dose at the discretion of the Investigator).
- 8. Physical examination should be performed at Randomization. Performed at Week 8, Week 24, and also at each Unscheduled Visit, only if medically indicated.
- 9. Vital signs (body temperature, heart rate, respiration rate, blood pressure, pulse oximetry, height, and weight) should be measured just prior to dosing on Day 1, Week 8, and also at each Unscheduled Visit (if medically indicated). Collection of vital signs at Week 24 should be performed if medically indicated and is at the discretion of the Investigator. Weight for wheelchair-bound participants is optional. Height is only required at Randomization.
- 10. Electrocardiograms should be performed at Screening in all participants, and at Weeks 8 and 24 if medically indicated and is at the Investigator's discretion.
- 11. Adverse events and serious adverse events will be collected from the time a participant signs informed consent through Week 24 and at Unscheduled Visits as described in Section 7.3. SAEs reported by participants within 30 days after completing Early Termination or Week 24 visit will be collected. In addition to collection of all AEs, the following AEs will be specifically solicited using a daily participant diary for 7 days following IP administration (Day 1 to Day 7): abdominal distention or bloating, chills/severe shivering, abdominal pain or cramping, increased diarrhea, constipation, nausea, vomiting, and fever. The diary will be reviewed at the Week 1 visit.
- 12. Prior antibiotic medication use should be recorded for the 28 days prior to Screening and all other medications for the 14 days prior to Screening. All concomitant medications at Screening and following dosing should be recorded through Week 24.
- 13. Females of childbearing potential enrolled in this trial will have serum hCG pregnancy testing administered during Screening. Additionally, a urine pregnancy test will occur at Randomization. The Investigator may repeat a urine pregnancy testing at any point during the trial as medically indicated. Females who are postmenopausal for ≥ 1 year or surgically sterile will not undergo pregnancy testing.

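### The AE exception for vital signs and physical examination names the Screening visit, where neither is scheduled, so Day 1 baseline findings can be recorded as AEs and, if untimed, counted as TEAEs

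*Protocol*

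**What the plan says.** Section 7.2.11 of the protocol: "Any physical examination finding that is judged by the Investigator as clinically significant (except at the Screening visit) will be considered an AE". Section 7.2.10 repeats the rule for vital signs: "Any vital sign abnormality that is judged by the Investigator as clinically significant (except at the Screening visit) will be considered an AE". Screening is the only visit that either section excepts.

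Table 3 (Part A) marks the physical examination at Day 1 only, and vital signs at Day 1, Week 8 and unscheduled visits. The Screening cell is empty in both rows. Footnote 8 says "Physical examination should be performed at Randomization", with later examinations only if medically indicated. Footnote 9 says that vital signs "should be measured just prior to dosing on Day 1, Week 8" and at unscheduled visits if indicated. Table 4 has the same pattern for Part B.

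Section 7.2.2, which defines AEs, says: "Disease signs, symptoms, and/or laboratory abnormalities already existing prior to the use of the IP are not considered AEs after treatment unless they reoccur" after recovery, or are a clinically significant exacerbation. Sections 7.2.1 and 7.2.3.1 start AE collection at informed consent.

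Section 8.5.2 defines a TEAE as an AE during or after IP administration and adds a default: "AEs occurring at Randomization (Day 1) with no associated onset time are assumed to be treatment-emergent". Section 3.3 lists TEAE incidence through Week 8 among the primary endpoints of Part A.

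**The concern.** An exception of this kind normally keeps baseline disease out of the AE record. Here it points to a visit at which neither assessment is scheduled, while the assessments that do serve as baseline fall on Day 1 and are not excepted. A site that follows 7.2.10 or 7.2.11 literally would record as an AE a finding that 7.2.2 tells it not to count. With about 100 sites planned, the two instructions may be applied differently from site to site.

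The missing-time default can then carry such a record into the primary safety endpoint. The default is a sensible conservative convention when it is truly unknown whether an event began before or after dosing. It is the wrong rule for a finding made at an assessment known to precede dosing.

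**Working it through.** The protocol states no figure on this point, so there is nothing to reproduce. The check compares the text with the schedule and then gives an illustration under stated assumptions.

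**Step 1. Does the exception cover anything scheduled in Part A?**

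| Assessment | Exception in the AE rule | Marked at Screening in Table 3 | First scheduled | Exception covers a scheduled assessment |
|---|---|---|---|---|
| Physical examination (7.2.11) | Screening | No | Randomization (Day 1) | No |
| Vital signs (7.2.10) | Screening | No | Day 1, before dosing | No |
| ECG (7.2.12) | Screening | Yes | Screening | Yes |

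The same parenthesis works for the ECG, which is done at Screening. It does not work for the other two.

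**Step 2. Does another section settle the matter?** Section 7.2.2 removes pre-existing signs from AEs after treatment and ties recording to worsening from baseline. Section 8.5 sets the safety baseline as the last assessment before IP. For vital signs that is the Day 1 measurement itself, and no earlier one is scheduled against which to judge worsening. Sections 7.2.10 and 7.2.11 are the specific rules, apply to any finding, and list one exception. The protocol does not say which section prevails, so this is an unresolved conflict.

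**Step 3. What must happen before a baseline finding is counted as a TEAE?** All of the following:

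1. The investigator judges it clinically significant.
2. The site follows 7.2.10 or 7.2.11 rather than 7.2.2.
3. The onset is dated Day 1, not earlier.
4. No onset time is recorded.

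If any one fails, the finding stays out of the TEAE count.

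**Step 4. Illustration of size.** Let p be the true TEAE proportion in an arm and q the share of participants who meet all four conditions. Take q as equal in both arms, because a finding made before dosing cannot depend on the treatment received, and as independent of having another TEAE. Then

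p′ = p + (1 − p)q, and p′₁ − p′₀ = (p₁ − p₀)(1 − q).

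Assume that all 324 are dosed, 216 on CP101 and 108 on placebo (2:1).

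| q (assumed) | p = 50% in both arms becomes | Extra participants with a TEAE (CP101 / placebo) | 60% vs 50%: the 10.0-point difference becomes |
|---|---|---|---|
| 1% | 50.5% | 1.1 / 0.5 | 9.9 |
| 5% | 52.5% | 5.4 / 2.7 | 9.5 |
| 10% | 55.0% | 10.8 / 5.4 | 9.0 |

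For example, at q = 10%: 0.50 + 0.50 × 0.10 = 0.55, and 216 × 0.05 = 10.8. The protocol gives neither q nor an all-TEAE rate; the PRISM3 rates in section 1.5.2 are for drug-related TEAEs only.

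**The case against.** The strongest reply is that the protocol can be read consistently. Section 7.2.2 is the general AE definition and already excludes pre-existing signs. A finding that is new between consent and dosing may properly be recorded as a pre-treatment AE, and 8.5.2 counts only events during or after IP. The default needs both a Day 1 onset and a missing time. The CRF is not shown and may capture the time, and under section 8.2 the SAP takes precedence on analysis details and may refine the rule.

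Much of this stands, and it rules out several stronger conclusions that a reader might draw:

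- *That pre-dose findings necessarily become AEs and then TEAEs.* The documents do not support this. Section 7.2.2 is a competing rule, and nothing in the protocol says that such findings usually lack an onset time.
- *That the examination is always before dosing.* Pre-dose timing is explicit for vital signs. The examination is placed only at Randomization in Part A and at IP administration in Part B.
- *That the arm comparison is biased towards one arm.* The inflation is non-differential. The visible text presents the primary safety endpoint by treatment group and states no test for it.
- *That Table 3, footnote 1 adds a second dating error.* IRT enrolment on the previous day is allowed only in extenuating circumstances with written Sponsor approval, and the dosing day is still called Day 1.

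The reply does not repair the wording. The exception still names a visit without the assessments, and sites must still choose between 7.2.2 and 7.2.10 or 7.2.11.

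**Conclusion.** The point holds as a conflict of wording that can feed a primary safety endpoint. The Screening-visit exception in 7.2.10 and 7.2.11 covers no scheduled vital signs or physical examination in Part A. Followed literally, it allows a Day 1 baseline finding to be recorded as an AE against 7.2.2, and 8.5.2 then counts the AE as treatment-emergent if it is dated Day 1 without a time.

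The expected effect is a small, non-differential rise in TEAE incidence in both arms, with any true difference shrunk by the factor 1 − q. The percentages in the illustration rest on assumed values of p and q and on independence; the true size cannot be derived from the protocol. Efficacy conclusions, alpha and power are not affected. The change is worth making because it is precise and nearly free.

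**What to change.** 1. In 7.2.10 and 7.2.11, replace the Screening-visit exception with one for findings at assessments made before IP administration, consistent with 7.2.2. Record such findings as medical history, or as a non-treatment-emergent AE if new since consent.
2. In 8.5.2, apply the missing-time default only to dosing-day events that were not found at a pre-dose assessment.
3. Apply the same wording to Day 1 of Part B.
4. If the CRF does not already capture it, record for each dosing-day AE whether it began before or after IP.

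The cost is a few words of protocol text and at most one extra field for sites to complete. No visit or procedure is added.

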# 7.2.12 Electrocardiograms

Single 12-lead electrocardiograms (ECGs) will be performed per SOC at the time points listed in the Schedule of Assessments (Table 3 and Table 4). Evidence of clinically significant abnormalities during the Screening visit may result in exclusion from the trial. A 12-lead ECG will only be performed at Week 8 and Week 24 if medically indicated and is at the discretion of the Investigator.

Any ECG abnormality that is judged by the Investigator as clinically significant (except at the Screening visit) will be considered an AE, recorded on the CRF, and monitored as described in Section 7.2.3.

